### 12.2 Statistical methods

Changes in imaging parameters and metabolomics patterns will be used for statistical inference. We also intend to apply multivariate data reduction and texture analyses techniques on multi-dimensional parametric images from the study population. In this part of the project a close collaboration is planned with the project of [name]. All data will be stored in communicating databases for future re-analyses when long-term follow-up data is available and new methods for multiparametric analyses become available. Contrary to many studies that result in "promising results" we aim to bring preliminary findings to a higher level of validation and thus prepare for large scale clinical studies. In

the clinical data sampling procedures a pre-determined fraction of the patients will be randomised and stored separately for hypothesis validation.

Survival endpoints will be compared by Cox regression stratified for tumor site and corrected for all other covariates used in the minimization algorithm – i.e. a multivariate Cox regression will be applied with tumour sites as strata as covariates

The primary analysis will be based on the intention-to-treat analysis set. Every effort will be made to collect survival data on subjects, including subjects withdrawn from treatment for any reason, who are eligible to participate in the study and who have not withdrawn consent for survival data collection. OS is defined for each patient as the time between radiotherapy start date and death. If a patient has not expired, the patient will be censored at the time of last contact (last known alive date).

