## 3 Background and introduction

### 3.1 Background

The knowledge of factors determining treatment effect in cancer therapy is important in the treatment selection for individual patients. In some cancers impressive progress has been made over the years and has resulted in major improvements in disease control, e.g. in breast cancer. The basis for treatment selection is usually the assessment of pre-treatment characteristics of the patient and the individual tumour. Expression of certain genes, hormonal status and proliferation parameters are some examples of individual tumour properties in clinical routine use. The development in the field of molecular biology during recent decades is not reflected in a similar improvement of therapeutic results for most cancers. Particularly this is the case with most SCCs. In Sweden about 2000 SCC are diagnosed every year within lungs, head & neck, anus, cervix and esophagus.

For a large proportion of cancers the knowledge of pre-treatment parameters of predictive capacity is sparse. A number of biomarkers or combinations thereof have been identified (e.g. HPV, EGFR, ...). In the majority of cases they correlate to outcome of treatment and can therefore be described as prognostic and not specific enough for personalised therapy. In the absence of strong predictors an alternative is to explore the early changes after initiating therapy. Such changes have the potential to be relevant in the assessment of individual tumour response. It is assumed that the changes will also give leads to factors present already before treatment, which are not yet identified.

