## **9 Study procedure**

### **9.1 Study entry**

#### **9.1.1 Mandatory investigations**

1. Adequate clinical assessment with a TNM classification and histology/FNAC (showing squamous cell carcinoma).
2. Body weight and height
3. ECOG Performance status
4. P-Creatinine

5. Tumour biopsy and blood sampling in patients participating in the exploratory part of the study.
6. Registration form including informed consent
7. The disease specific module of the EORTC QLQ-C30 for reporting late RT effects should be offered for the patient to fill out and forward to the data centre in a pre-stamped envelope. With the exception of sites where no such module is available.

Investigations number 1-4 are clinical routine investigations, and are thus not regarded as study specific procedures.

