## 12 Statistical plan

### 12.1 Sample size determination

From the expected number of eligible patients with each diagnose, three separate study groups are identified

1. Lung cancer
2. Head and neck cancer
3. Cervix, esofagus and anal carcinoma

The first two subgroups will be analysed separately as well as aggregated with all other groups. In group no 3 the number of patients with each diagnosis is expected to be too low to make valid statements for each entity. This group will therefore mainly be analysed together with all cases.

The overall aim of the study is to identify and validate parameters predictive to outcome of treatment. To estimate the degree of agreement, the Cohen's Kappa is commonly used. It is defined as the proportion on the main diagonal that exceeds the expected number if a random classification is performed. It is normalised to fit the interval (0,1) where 0 is a random classification and 1 is a 100% correct classification.

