For personalised therapy purposes a correct classification in 90 % of cases is desired. We assume that the proportions of responding patients are either distributed similarly (50 %/50 %) or that only 20 % are responders.  $H_0: k = k_0$ ,  $H_1: k = k_1$ ,  $k_1 > k_0$ . Assuming  $k_0 = 0.4$  (which is considered to indicate a poor agreement) and  $k_1 = 0.7$  (which is considered to indicate a good agreement) and if the probability of correct rejection of  $H_0$  is set to 90 % the number of patients needed is 63 or 80 depending on response rates (50 % or 20 %). Thus, a number of patients of about 70 for each study group should be optimal to answer the study questions. In addition to the 70 patients of each group, the data from 30 patients from the head and neck cancers and lung cancers will be used for hypothesis generation. Their data will not be re-used for validation. From previous experience, a proportion of patients will for medical or other reasons not contribute with the second set of data. It is assumed that 20% of patients will have incomplete data sets. Thus, the number of included patients in each group will be aimed at 100. Additionally, the 30 first patients will be part of a pilot study and not analysed further for the study end-points. The total number of patients needed for the study is estimated to 412 during the three years of accrual. However, each group will be closed earlier for further inclusion if 100 evaluable patients are reached. Image and bio-marker analyses will be performed only on those with complete data sets from imaging sessions.

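### The kappa test against a fixed 0.4 does not ask whether early change adds to baseline stage, performance status and first scan, so a marker that mirrors baseline prognosis could pass

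*Protocol*

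**What the plan says.** Protocol 12.1 gives the aim: "The overall aim of the study is to identify and validate parameters predictive to outcome of treatment". Agreement is measured by Cohen's kappa. The null value is 0.4, "which is considered to indicate a poor agreement", and the alternative is 0.7, "which is considered to indicate a good agreement". Power is 90%, and about 70 patients per study group are taken as sufficient. No significance level is stated.

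Protocol 12.2 names the predictors: "Changes in imaging parameters and metabolomics patterns will be used for statistical inference". Its only covariate adjustment is a Cox model for the survival endpoints, stratified by tumour site and corrected for the covariates of a minimisation algorithm. This non-randomised study has no such algorithm, so no baseline covariate other than site is actually named.

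The baseline data exist. Section 9.1.1 makes mandatory "Adequate clinical assessment with a TNM classification and histology/FNAC (showing squamous cell carcinoma") as well as ECOG performance status, and section 7 places the first imaging session within two weeks of the planned start of radiotherapy.

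Section 3.1 says "A number of biomarkers or combinations thereof have been identified (e.g. HPV, EGFR" and others). It adds that most of them only correlate with outcome, and treats that as prognostic information too unspecific for individualising treatment.

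**The concern.** The reason for a second assessment during treatment is that early change should tell us something the pre-treatment picture does not, and section 3.1 argues in those terms. A test against a fixed kappa cannot show this. Bulky or advanced tumours may both change less and fail more often. A change parameter that carried no information beyond stage or baseline uptake would then agree with outcome as well as those factors do, and the test would credit it.

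The second session costs the patient a further FDG exposure (about 10 mSv by section 15.5.1) and, where applicable, another biopsy. Whether it adds information is therefore a central question, and the plan as written leaves it unanswered.

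**Working it through.** **Inputs.** From 12.1: null kappa 0.4, alternative 0.7, power 90%, responders 50% or 20%, about 70 patients per group, three groups (3 × 70 = 210 pooled). Assumed: one-sided 5%, because the alternative is written as one-sided and no level is given. Also assumed: baseline kappa of 0.3 to 0.7, because the documents give none.

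**Variance.** For a binary rating with equal marginals and responder proportion p, the large-sample variance of the estimated kappa is Q(k)/n, with

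Q(k) = (1−k)·[(1−k)(1−2k) + k(2−k)/(2p(1−p))].

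At p = 0.5 this reduces to 1−k². Hence Q(0.4) = 0.84 and Q(0.7) = 0.51 at 50% responders, and 1.272 and 0.817 at 20%.

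**The protocol's own figure.** It says "the number of patients needed is 63 or 80 depending on response rates (50 % or 20" %). With n = [(1.645·√Q(0.4) + 1.282·√Q(0.7))/0.3]²:

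- 50% responders: [(1.508 + 0.915)/0.3]² = 65.2, so 66.
- 20% responders: [(1.855 + 1.158)/0.3]² = 100.9, so 101.

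The stated 63 has 88.9% power and the stated 80 has 82.0%. None of the variants tried (one- and two-sided, several levels and powers, other variance formulas) gave both 63 and 80. This is a side point: the size of the present concern depends on the fixed 0.4 and on about 70 patients.

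**Threshold for passing.** The observed kappa must exceed 0.4 + 1.645·√(Q(0.4)/n):

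- n = 70: 0.4 + 1.645·√(0.84/70) = 0.580 at 50%; 0.4 + 1.645·√(1.272/70) = 0.622 at 20%.
- n = 210: 0.504 and 0.528.

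**Chance that a perfect copy of baseline passes.** This is P(observed kappa > threshold) with standard error √(Q(k)/n). For example, at k = 0.6, 50% responders and n = 70, the standard error is √(0.64/70) = 0.0956 and (0.580 − 0.6)/0.0956 = −0.21, giving 58%.

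| Assumed baseline kappa | n = 70, 50% / 20% responders | n = 210, 50% / 20% |
|---|---|---|
| 0.3 | 0.7% / 0.9% | 0.1% / 0.2% |
| 0.4 | 5% / 5% | 5% / 5% |
| 0.5 | 22% / 17% | 47% / 35% |
| 0.6 | 58% / 43% | 96% / 85% |
| 0.7 | 92% / 77% | about 100% / 99.7% |

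**Sensitivity.** At two-sided 5% and n = 70, the thresholds are 0.4 + 1.96·√(Q(0.4)/70) = 0.615 and 0.664, and the rates at kappa 0.6 fall to 44% / 30%. Simulation at n = 70, one-sided, gave 57% / 41% at kappa 0.6 and 90% / 72% at 0.7. When noise lowered the copy's average kappa from about 0.60 to about 0.54, its pass rate fell from 57% / 41% to 33% / 25%.

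**What a comparison with baseline would need.** As an illustration, take a paired McNemar test (two-sided 5%) of a marker with 85% accuracy (kappa 0.7 at 50/50). Power is Φ[(δ√n − 1.96√d)/√(d − δ²)], where δ is the accuracy difference and d the discordance. Let d run from its minimum, δ, to conditional independence, for example 0.75·0.15 + 0.85·0.25 = 0.325.

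| Baseline accuracy (kappa) | d | Power, n = 70 | Power, n = 210 |
|---|---|---|---|
| 70% (0.4) | 0.15 to 0.36 | 92% to 55% | about 100% to 96% |
| 75% (0.5) | 0.10 to 0.325 | 77% to 31% | 99.7% to 72% |
| 80% (0.6) | 0.05 to 0.29 | 46% to 12% | 91% to 27% |

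A single group of 70 is enough only in the most favourable case. The pooled set is the realistic place for the comparison.

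**The case against.** Reference models and added-value measures are often left to a statistical analysis plan, which is not at hand, and nothing in section 12 forbids a baseline comparison. That is fair. But the hypothesis, the benchmark and the sample size are fixed in the protocol without one, and the power figures show that such a comparison bears on the design.

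Four stronger readings are tempting and not supported:

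- A reader might infer that a baseline mirror would be validated. It could be. If baseline kappa is 0.4 or lower, it passes at most about 5% of the time. Section 3.1 itself calls knowledge of pre-treatment predictors sparse, which makes high baseline kappas less plausible.
- A reader might infer that only changes are analysed. Section 12.2 says changes will be used, not that nothing else will be. Section 12.4 searches the hypothesis generation group for predictive parameters generally.
- A reader might take this as the primary-endpoint analysis with 0.4 as the pass mark. Kappa 0.4 against 0.7 is the sample-size hypothesis. It speaks of responders, is not tied to two-year loco-regional control, and stands beside a wish for 90% correct classification.
- A reader might infer that useful markers with modest kappa are discarded. The only dropping rule, in the Synopsis under Interim analysis, concerns parameters that show no rapid change.

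Finally, the stated aim is prediction of outcome, which kappa does address. Making added value a condition for any claim would be a preference, and a group of 70 could reject real markers for lack of power. That part of the objection stands and limits the fix.

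**Conclusion.** The point holds as a gap in what the validation can show. The protocol's one formal hypothesis measures agreement with outcome against a fixed value. No section sets the early changes against the baseline data already collected, although section 3.1 draws the distinction between merely prognostic and usefully specific markers.

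The size depends on an unknown. The risk is negligible if baseline factors reach kappa 0.4 or less, moderate at 0.5 (17% to 22% per group) and substantial at 0.6 or more (43% to 92%). Pooling raises it above 0.4. These figures assume a one-sided 5% level, equal marginals and a perfect copy of the baseline classifier; a noisy copy passes less often. Whatever the baseline kappa, a pass on its own cannot support a claim that the second assessment adds information.

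**What to change.** In 12.2, for the same binary outcome as the kappa test:

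1. Fit a small reference model in the pooled hypothesis generation group and lock it before validation: site, stage and the baseline value of the imaging parameter, with ECOG status only if numbers allow. Depending on how 12.1 (30 patients from head and neck and lung, in total or each) and 12.4 (one in four; 300/4 = 75 of the planned evaluable patients) are read, that group has roughly 30 to 75 patients. At 20% responders this is 6 to 15 responders, so a longer covariate list is not supportable.
2. In the pooled validation set, report the reference model's kappa beside the marker's. As a pre-specified key analysis, test whether early change improves the reference model (likelihood-ratio test, with the difference in AUC and its confidence interval). Because the locked model rests on few patients, repeat the test with the baseline terms refitted in the validation set.
3. Keep the kappa test for the statement that a marker predicts outcome. Let the added-value result decide how any claim of extra early-response information is worded.
4. Within single groups of about 70, give estimates with confidence intervals and do not rely on the test.

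The cost is analysis wording and one further model on data already collected. The downsides are limited power for added value within a group, and that fewer markers may be described as adding to baseline.

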## **5 Study design**

The study is prospective, multi-centre, non-randomised observational study for investigation and validation of imaging biomarkers for early treatment response. Patients are recruited with previously untreated SCCs aimed for radiotherapy with curative intent of the oral cavity, oropharynx, uterine cervix, oesophagus, anal canal or lung. Multimodal, functional imaging data are collected before and during the early phase of radiotherapy. In parallel to the imaging data, tumour biopsies and blood will be collected for molecular analyses that may provide explanatory information to the imaging information.

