### **12.3 Subject Population(s) for Analysis**

Intention to treat population: Any subject included in the study, regardless of whether they received planned treatment.

Protocol-compliant population: Any subject who was randomized and received the planned treatment.

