### **12.4 Pilot study**

The first 20-30 patients will be part of a pre-study where the timing and protocols for investigation are optimised. These patients will not be included in the analysis of the main study. One of four patients will be randomly chosen for belonging to the “hypothesis generation group” (HGG). Their data will be analysed in the search of a number of predictive parameters for outcome. The remaining patients’ data will be used for validation of hypotheses. The HGG will not be used in this validation process. The first analyses will be performed when the number of study patients is reached. The second analysis will be performed two years after including the last patient. The third analysis will be performed when five years have passed since the last inclusion of a patient.

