## **14 Data management**

### **14.1 Patient registration procedure**

Subject eligibility will be established before inclusion. Subjects will be given a identification number consecutively, as subjects are eligible for enrolment.

If a subject discontinues from the study, the subject number will not be reused, and the subject will not be allowed to re-enter the study.

The Data Centre (CTU, Norrlands universitetssjukhus) is responsible for the registration procedure. When a patient is found to be eligible and has signed a written informed consent, registration will be performed via the study coordinating person.

A registration form should be filled out before inclusion of each patient. This form will contain all relevant data on the patient

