## 15.5 Risk-benefit analysis

Since the treatment of each patient's disease will not be affected by the assessment procedure or the results of it, the risks are limited to the imaging and biopsy procedures.

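### The survival models are to be corrected for the covariates of a minimization algorithm that the protocol does not contain, so tumour site is the only adjustment factor that can be identified

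*Protocol*

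**What the plan says.** Section 12.2 gives one rule for the survival analyses: "Survival endpoints will be compared by Cox regression stratified for tumor site and corrected for all other covariates used in the minimization algorithm". The clause that follows, meant to spell this out, reads "a multivariate Cox regression will be applied with tumour sites as strata as covariates". It names no factor other than site and gives site two roles in one phrase. The same section says what the inference is about: "Changes in imaging parameters and metabolomics patterns will be used for statistical inference".

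The design sections give no allocation procedure:

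- Section 5: "The study is prospective, multi-centre, non-randomised observational study".
- Section 14.1: "Subjects will be given a identification number consecutively, as subjects are eligible for enrolment".
- Section 15.5 says that treatment of the patient's "disease will not be affected by the assessment procedure or the results of it".

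Two random draws are mentioned. Section 12.2 sets aside a pre-determined fraction of patients for validation. Section 12.4 draws one patient in four into a hypothesis generation group, of which it says: "Their data will be analysed in the search of a number of predictive parameters for outcome". Neither draw lists a balancing factor.

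Section 12.3 has a similar slip. It defines the protocol-compliant population as "Any subject who was randomized and received the planned treatment".

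**The concern.** A minimization algorithm is an allocation method with a stated list of balancing factors, and adjusting for those factors afterwards is standard in a randomised trial. Here the protocol uses the reference to define its adjustment set, but the list it points to is not in the document. The protocol therefore does not leave the covariates open for a later plan; it fixes them by a rule that cannot be followed. An analysis plan that keeps to the sentence has nothing to copy, and one that lists covariates has to depart from it.

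The endpoints concerned are secondary: PFS at 2 years and OS at 2 and 5 years (section 4.2.2). In an observational marker study, adjustment is the main protection against a marker that only stands in for stage or performance status. Stratifying by site does not provide it. If the covariates are instead chosen once outcomes are known, the validation that section 12.2 aims for is weakened.

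**Working it through.** **Step 1: the text.** The plan gives no figure to reproduce, so the first check compares passages.

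| Possible source of minimization factors | What the protocol gives |
|---|---|
| Treatment allocation (5, 10, 15.5) | None; non-randomised, treatment by local routine |
| Registration (14.1) | Consecutive numbers, no factors |
| Validation fraction (12.2) | Random, no factors |
| Hypothesis generation group (12.4) | One in four at random, no factors |
| Restatement of the model (12.2) | Tumour site only |

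One adjustment factor is named and no minimization covariates can be identified. Even site is open: section 8.1 lists six sites, section 12.1 forms three study groups.

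**Step 2: what site strata alone would leave.** From the protocol: 70 complete data sets in each of three groups (12.1), so 3 × 70 = 210. Everything else is assumed: hazards of 0.15, 0.25 and 0.35 per year in the three groups, administrative censoring only, stage HR 1.25, 1.5 or 2.0 per SD, and marker–stage correlation *r* from 0 to 0.4. The marker has no effect of its own. Each cell has 2000 simulations of a stratified Cox model with a two-sided 5% Wald test (Monte Carlo SE 0.5–1.1 points).

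Events by 2 years at average stage: 70 × [(1 − e^−0.30) + (1 − e^−0.50) + (1 − e^−0.70)] = 70 × (0.259 + 0.393 + 0.503) ≈ 81. The spread in stage raises this to about 82–86.

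Share of runs in which the marker is significant, site strata only, 2 years:

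| *r* | HR 1.25 | HR 1.5 | HR 2.0 |
|---|---|---|---|
| 0 | 5.6% | 5.1% | 5.1% |
| 0.1 | 5.5% | 6.5% | 8.3% |
| 0.2 | 6.6% | 10.4% | 21.0% |
| 0.3 | 9.1% | 18.7% | 40.4% |
| 0.4 | 12.8% | 29.7% | 62.5% |

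With stage added in four groups, all cells lie between 5.2% and 6.8%; with stage in two groups, between 5.1% and 15.3%.

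**Hand check.** With stage omitted, the marker's log hazard ratio is roughly *r* × ln(HR), so its *z* statistic centres near *r* × ln(HR) × √D, with D the number of events. For *r* = 0.2, HR 1.5, D = 83: 0.2 × 0.405 × 9.11 = 0.74. Then P(|Z + 0.74| > 1.96) ≈ 0.11, against 0.104 simulated. The approximation overshoots in the strongest cell (0.4 × 0.693 × √86 = 2.57, giving about 0.73 against 0.625), because leaving out a strong covariate also shrinks the estimate.

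**Step 3: variants.** Weak, middle and strong are (*r*, HR) = (0.1, 1.25), (0.2, 1.5) and (0.4, 2.0). The ECOG rows also assume 40% of patients at ECOG 1 or more, HR 1.5, a marker–ECOG latent correlation of *r*/2 and a stage–ECOG correlation of 0.2. The six-site row assumes sizes 35/35/70/24/23/23 and hazards 0.12–0.40.

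| Setting | Events | Site only: weak / middle / strong | Adjusted: weak / middle / strong |
|---|---|---|---|
| 5 years, stage in 4 groups | 141–144 | 5.0 / 15.0 / 78.3% | 5.1 / 4.7 / 7.3% |
| 2 years, stage + ECOG | 92–96 | 5.9 / 14.2 / 73.0% | 4.8 / 5.8 / 6.4% |
| 5 years, stage + ECOG | 150–155 | 7.0 / 19.6 / 85.7% | 5.9 / 6.0 / 7.9% |
| Six-site strata, 2 years, stage + ECOG | – | 6.2 / 13.6 / 73.8% | 5.6 / 5.5 / 5.7% |
| One group, n = 70, hazard 0.25, 2 years, stage in 2 groups (no site strata) | 28–30 | 6.1 / 7.3 / 25.6% | 6.1 / 6.5 / 8.8% |

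**The case against.** The strongest reply is that this is leftover wording from a randomised-trial template. The authors plainly meant to adjust, so the real consequence is an undefined covariate list, not the site-only model simulated above. That is fair: the simulations show what is lost if only the identifiable factor is used, and do not measure the effect of a freely chosen list.

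Second, the percentages are not type I error for every question. The protocol's aims are to correlate imaging data with outcome and to validate predictors; they do not claim independence from stage. A marker correlated with stage is truly associated with survival, so finding that association is no error. The figures are false positives only for the claim that the marker adds something beyond stage or performance status. That limit stands and must be read with them.

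Third, every driver of the size is assumed, and one set of hazards serves for both PFS and OS. This also stands, and it is why only a range is given.

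Fourth, the data split might have been minimised on factors listed in a plan not shown. Section 12.4 describes a plain random choice, which makes this unlikely without excluding it. The restating clause is also ungrammatical and may have lost words, but the defect in the main sentence does not depend on it.

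None of this gives the sentence a list to refer to.

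**Conclusion.** The concern holds. The adjustment set is defined by reference to a procedure the protocol does not contain, and tumour site is the only factor that can be identified. That conclusion rests on the text alone. It touches secondary endpoints only, reading survival endpoints as PFS and OS, the only ones so named. It should be corrected.

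The practical size is uncertain. Under the assumed hazards, site strata alone are close to nominal when the marker is weakly related to stage. They are far from it when the relation is strong: up to 63% at 2 years and 78% at 5 years with stage alone, and 86% at 5 years if the marker also tracks ECOG status. Adjusting for stage in four groups, with ECOG where it matters, brings the pooled analysis to about 5–8%.

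**What to change.** Replace the sentence in section 12.2 with text along these lines:

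> PFS and OS will be analysed by Cox regression on the imaging or metabolomic predictor or predictors fixed in the hypothesis generation group. The pooled analysis is stratified by tumour site (the six sites of section 8.1) and adjusted for baseline TNM stage and ECOG performance status. The separate lung and head-and-neck analyses use a sparser set, for example TNM stage in two groups. Groupings are fixed before outcomes are analysed.

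If the three groups of section 12.1 are meant as strata, say so instead; six and three strata gave nearly the same results. Drop both the reference to minimization and the phrase that makes site stratum and covariate at once. In section 12.3, change randomized to included. The minimum correction is to remove the reference and list the covariates; the particular set above is a proposal.

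The cost is a few sentences. TNM and ECOG are mandatory at entry (section 9.1.1). HPV, mentioned in the background, is not a listed entry investigation and so is not proposed. With one predictor, the pooled model has 1 + 3 + 1 = 5 parameters on about 82–96 events by 2 years at the assumed rates: 82/5 ≈ 16 to 96/5 ≈ 19 events each. Each further predictor adds one parameter. The separate models have 2 parameters on about 28–30 events, or 14–15 each.

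The downside is that coarse stage groups leave some residual confounding: up to 9% of runs significant at n = 70, and up to 15% if two groups were used in the pooled model.
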